### **Personalised Care Plan**

In this circumstance the care plan is a plan that assists the client in monitoring his or her own health, and will be the basis from which the nurse monitors the client's health status. The plans are personalised in that the limits and details to be monitored (signs and symptom) are set for the particular individual by the specialist treating team. The plans enable both client and health team to monitor their health status on a daily basis, act on any variables in their health by providing instructions on how to identify changes in health status and how to respond to these changes to prevent further deterioration. The care plan is structured as such that, unlike many care plans commonly used, it will contain within it identifiers for escalation of either treatment by the client themselves and/or flags to the health professional that intervention maybe required.

### **In Hours Daily Care and Escalation**

In line with the client's care plan, clients will record information in the system initially on a daily basis. This information will be monitored by the nurse. If the client does not log in or has a result that is outside the set care plan parameters the nurse will:

- Call the clients and trouble shoot the issues over the phone,
- video call face to face if circumstances indicate a visual need or
- Arrange to conduct a home-based visit if indicated.
- If patient condition warrants escalated intervention the nurse will make contact with the appropriate consultant seeking further directions.

### **Compliance:**

As patients, nursing and medical teams become more familiar with each other, daily assessment may be adjusted according to need i.e. 2nd daily. Should client compliance drop below 70% of planned participation a phone call initially and/or a visit by a member of the program team to occur to understand reasons. Continued non-compliance will eventuate in the client ceasing to be part of the trial resulting in a return of telehealth devices and cessation of contact /visits. Notification of a client's leaving/ removal from the pilot study will be documented and reported to program team and HREC

**Clients will be advised and reminded/reinforced throughout the pilot study period that at any time they feel they require emergency care they should follow their usual practice (e.g call 000, ambulance, present to ED).**

The current Barwon Health Community Nursing Protocols and Policies ensuring staff and client safety will be utilised to guide all home based visits.

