### **Study Plan**

400 adults identified to be at a higher risk of readmission to hospital within the next 12 months who agree to participate will be randomised to either the intervention “usual care plus Personalised Health Care” group or the “usual care” control group. Patients in the intervention and control groups will be asked to participate for 12 months. Measures of hospital utilization and health literacy \ self-management will be measured at baseline and after 12 months of the intervention to determine if hospital utilization has decreased and if health literacy has increased for the intervention group.

*Usual Care control group* - Patient manages health condition as directed by usual and existing medical services, no limitations on care type that can be newly administered during the 12 months. Measures of Hospital Utilization, Health Literacy, self-management QOL at 0 and 12 months.

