### **Personalised Health Care Remote Patient Monitoring System**

The Remote Patient Monitoring (RPM) system used in this pilot project is a web based platform that can be accessed from any internet connected device. The patient, when accessing the platform, will be directed to their personalised care plan that has a questionnaire designed to educate and guide the client to monitor and support their own health. The peripheral devices that link to the system, enable the monitoring of clinical signs and symptoms such as SaO2, blood pressure and blood glucose measures.

For the health service clinicians accessing the platform, the RPM system identifies in real time which clients have recorded results at that point in time and which have not, it provides an indication of which results are at variance to the result parameters set for each individual, thus enabling a rapid and timely response.

The RPM system generates individualised reporting that allows the clinicians to monitor trends within a client's health care over time, enabling treatment to be appropriately adapted as and if required.

The client is required to log in to the system daily, to answer questions about their health and monitor aspects of their health. If clients do not complete their daily monitoring, the RPM system will alert the health service clinicians to this for follow up. The model is only as effective as the level of participation of the client, therefore for clients that are not willing or able to participate by choice or otherwise will need to be identified early, be removed or request to withdraw from the study.

Clients may choose to use their own web connected device to access the RPM system or alternatively Barwon Health will provide a suitable hardware device. If clients choose to use their own internet connected device, appropriate screening will be performed to ensure the device is suitable for purpose, including the quality of internet connectivity at the client's location. Client's using their own internet connection will be reimbursed at an appropriate rate for the amount of data transferred for the purpose of their RPM according to the data rates identified by the preferred vendor. If required Barwon Health will reimburse Internet costs or pay for new connections. If connectivity is not possible due to a patient's residential location, patient will be excluded from participation

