**Data Storage/Record Retention**

Data	Pre and post measures of	Intervention	Control	Monitor only	Program Evaluation	Source
Length of Stay (LOS)	LOS or average LOS(s) at hospitalisation	✓	✓	✓	✗	Data Ware-House

Hospital Admissions	Number of hospitalisations in past 12 months	✓	✓	✓	✗	Data Ware-House	F v f c E f
ED Presentations	Number of ED presentations in past 12 months	✓	✓	✓	✗	Data Ware-House	F v f c E f
Quality of Life	Specific validated questionnaire	✓	✓	✗	✗		F v f c E f
Health Literacy \ Self management	Specific validated questionnaire	✓	✓	✗	✗		F v f c E f
Mortality		✓	✓	✓	✗	Hospital Data	F v f c E f
PRaDA	Predictive value of the patients (intervention vs control vs followed)	✓	✓	✓	✗	PRaDA	F v f c E f
Interviews	NA	✗	✗	✗	✓	Word files/PDF password	

						protected
--	--	--	--	--	--	-----------

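### Clients who do not keep up monitoring leave the trial itself, after randomisation and in one arm only, and the protocol does not say they are still followed or analysed as allocated

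*Protocol*

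**What the plan says.** Two places in Section 8 of the protocol set the rule.

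- **Compliance.** "Should client compliance drop below 70% of planned participation a phone call initially and/or a visit by a member of the program team" follows, to find out the reasons. If the problem persists, "Continued non-compliance will eventuate in the client ceasing to be part of the trial", with the devices handed back and an end to contact and visits. The same paragraph then speaks of leaving or removal from the pilot study, which is to be documented and reported to the program team and the HREC. How long non-compliance must last to count as continued is not stated.
- **Personalised Health Care Remote Patient Monitoring System.** Clients "not willing or able to participate by choice or otherwise will need to be identified early, be removed or request to withdraw from the study".

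The task behind both rules belongs to one arm. In the intervention arm, "The client is required to log in to the system daily, to answer questions about their health and monitor aspects of their health". In the control arm, under Study Plan, "Patient manages health condition as directed by usual and existing medical services".

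Allocation is made when the consent form is signed (Section 10, Participant numbers), and the monitoring system is set up at a later visit (Section 8, Follow-up visit). The Informed Consent section lets any participant leave at any time, in either arm.

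Admissions, length of stay and ED presentations (for example "Number of ED presentations in past 12 months") are listed for both arms with the hospital data warehouse as source (Data Storage/Record Retention). The AQoL, the Health Education Impact Questionnaire and the clinical measures are repeated at 12 months (Section 6). Retention and compliance with self-reporting are themselves study aims (Section 2).

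**The concern.** A randomised comparison is protected by keeping everyone in the arm to which they were allocated. Here staff can take a participant out of the trial after allocation because of behaviour that can be observed only in the intervention arm. No control can be removed for the same reason. If removed clients differ in prognosis and their outcomes are not counted, a selected remainder of the intervention arm is set against a control arm that has not been selected in this way.

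The hospital-use outcomes need no device and no contact, so nothing practical requires losing them. The 12-month questionnaires and clinical measures do need contact, and the Compliance rule ends it. A later analysis plan can define an analysis set, but it cannot recover assessments that were never made.

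The feasibility results are affected as well. Compliance and retention are meant to inform a full trial, and a rule that takes non-compliers out changes what both figures mean.

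**Working it through.** The protocol gives no expected removal rate, effect size or power, so there is no figure to reproduce. What follows is an illustration.

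**Inputs from the protocol:** 200 per arm; eligibility at a predicted 12-month admission risk of 0.5 to 0.8 (Selection Criteria).

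**Assumptions:** no true effect; a fraction f of the intervention arm is removed and left out of the analysis; d is the admission risk of removed clients minus that of retained clients.

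**Admission difference.** Overall risk is p = (1 - f) × p_retained + f × (p_retained + d) = p_retained + f × d. The spurious difference, intervention minus control, is therefore p_retained - p = -f × d.

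| f | d | -f × d |
|---|---|---|
| 10% | +0.10 | -1.0 point |
| 20% | +0.15 | -3.0 points (0.62 against 0.65 if p = 0.65) |
| 30% | +0.20 | -6.0 points |
| any | 0 | 0 |
| 20% | -0.10 | +2.0 points, against the program |

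**Scale.** The 95% half-width for a difference with 200 per arm is 1.96 × √(2p(1 - p)/200): 9.8, 9.3 and 7.8 points at p = 0.5, 0.65 and 0.8. With 140 against 200 (f = 30%) and p = 0.65 it is 1.96 × √(0.65 × 0.35 × (1/140 + 1/200)) = 10.3 points. Every scenario above lies inside the half-width.

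**Compliance.** Assume 85% in retained and 40% in removed clients. Over everyone allocated, compliance is (1 - f) × 85% + f × 40%: 80.5%, 76.0% and 71.5% at f = 10%, 20% and 30%. Computed only in those who remain, it is 85% each time.

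**Retention.** With no other loss, intervention retention is 1 - f: 90%, 80% and 70%. Removals counted as losses lower it.

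**After the fix.** If all 400 are followed to 12 months and compared as allocated, no one is left out because of removal, and this source of bias is zero whatever the excess risk d.

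**The case against.** The strongest reply is that nothing says removed clients are dropped from the analysis. The Compliance section lists return of devices and an end to contact and visits. It does not say that hospital data stop, and those data need no contact. The analysis set and the compliance denominator commonly belong in an SAP, which was not available for this review. The consent form, also not available, may cover use of data after leaving. All of this stands, and it means that bias in admissions, ED presentations and length of stay is conditional. It does not rescue the 12-month questionnaires and clinical measures, and it does not alter wording that ends membership of the trial.

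A reader might go further and infer that the results are biased in the program's favour, retention included. The documents do not support that.

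- They give no prognosis for non-compliers. Clients who feel well may also stop logging in, and then the sign reverses.
- There are reasons to think removed clients could be sicker. The rule reaches those unable to take part, and no passage says whether inpatient days are excluded from the 70% threshold, so an admission could itself lower compliance. That makes the direction plausible, not established.
- For retention, removals counted as losses work against the program. Retention would look better only if removed clients left the denominator, which no passage says.

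It is also fair that this is an unpowered pilot with no significance tests, that the planned confidence intervals are within each group, and that removals must be documented and so are traceable. This limits the consequence. Even so, the Study Plan sets out to determine whether hospital use has decreased, and Section 9 has the DSMB monitor the difference between groups.

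**Conclusion.** The point holds as a risk built into the rule, not as a demonstrated bias. The protocol takes continuously non-compliant, unwilling or unable clients out of the trial rather than only out of the service. This happens after randomisation and, for non-compliance with monitoring, only in the intervention arm. No passage provides for follow-up or analysis as allocated. Attrition can therefore differ between arms, and the resulting bias plausibly but not certainly favours the program.

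The illustrative range of -1 to -6 points rests entirely on assumed removal rates of 10% to 30% and an assumed excess risk of 10 to 20 points. It applies only if removed clients' outcomes are left out. Inflation of compliance is likewise conditional, on using only those who remain as the denominator. Retention is blurred because staff decisions and patient choice are counted together.

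**What to change.** Leave aside when the program stops monitoring, which is not judged here. In both Section 8 passages, state that stopping the telehealth service is not leaving the trial, and then:

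- keep every participant in the trial unless consent is withdrawn;
- collect data warehouse outcomes and the 12-month questionnaires for all randomised participants who have not withdrawn consent;
- compare the arms as allocated;
- report compliance with all clients allocated to the intervention in the denominator, and say how days after a service stop are treated. Counting them as non-compliant is one option; reporting compliance up to the stop, with stops shown alongside, is another;
- report staff-initiated service stops separately from withdrawal of consent.

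The cost is a change to protocol and consent wording and some extra 12-month follow-up of people no longer monitored. The hospital data already come from existing systems. A small downside is that the effect estimate will include non-users and may look smaller.

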### **After hours Coverage and Escalation**

After hours are defined as after 5:00 pm and before 8:00am The only variance to the system between in hours and after hours is the staff will be the After Hours Community Nurse, and the escalation process for staff will be as per the McKellar After hours roster.

The service will be supported by a 24/24 on call system which during Monday-Friday 8am-5pm will be the BH Personalised Health Care team and after hours will be a rotating roster of on call PHC staff. Staff providing the after-hours support will be able to electronically access both the BH Personalised Health Care system and the BH Digital Medical Record to ensure care advice is appropriate and documented as per standard BH protocols. Training will be provided to the after Hours Community Nurse Coordinator and appropriate ED staff.

In line with other services within CH&RS the escalation process will be firstly to the Service Coordinator, then to the relevant expert consultant if the matter is clinical and unable to be resolved by staff, and finally to the Executive Director of CH&RS. If there is a system issue, that requires immediate attention, escalation will be directly to the Executive Director of CH&RS. The IT escalation protocol will be as per all current clinical Information Systems.

Escalation after-hours will be directed to the already existing McKellar After Hours Manager (who is based at the McKellar site) and then to the Director On- Call. Please refer to the flow chart attached in appendix C for more detail

#### **Exit Strategy post Personalised Health Care program**

Patients will be monitored for a 12-month period of time. Following this period if a client's health remains unstable they will continue to be monitored via this service. If for any reason the service ceases to exist then clients will be referred to the appropriate BH community based program for their circumstance and care needs. That will be one (or more) of either

- HARP- for ongoing intensive case management and care coordination
- Primary Care- for interventional community based services
- Community Nursing Services – for home based nursing services

These clients are already supported by the health system, both acute and ambulatory sectors of the service. There is no risk to the ongoing care of these clients of for any reason the pilot program ceases to operate following the period of the research.

This service is providing monitoring over and above the standard care that patients currently receive. If the clients condition worsens to the point that they can not be monitored safely at home then they are likely to be receiving in-patient hospital treatment. The treating specialist consultant will determine the need for a hospital admission.

With the exception of the HARP program, clients will not be excluded from any other community based support programs if their needs indicate eligibility.

Following completion of the pilot program there are 3 possible outcome scenarios predicted as indicated below:

- The client has an improved ability to self-manage their own disease and does not require on-going daily monitoring and support, therefore they are 'discharged' from the pilot and their care followed up via BH Outpatients and their own General Practitioner.
- The client requires ongoing daily monitoring and the pilot project is successful and moves into a sustained program model, in which case the client will be monitored by the service.
- The client requires ongoing monitoring however the pilot project is ceased. In this situation the client will be referred to the HARP program for intensive case management and coordination, monitored via BH outpatients and their General Practice as per a clients normal management. If the client requires ongoing home based nursing support they will also be referred to the BH Community Nursing Program.

#### **9. SAFETY EVALUATIONS**

There are no known risks to participating in this study. The results will help determine initial effectiveness of personalised care plans, an associated all hours escalation process and remote

monitoring of your health using remote patient monitoring devices whereby results and information is entered/uploaded into a BH data storage site. From here, health care staff will be able to monitor patient health and provide care with increased efficiency.

### **Adverse events and Quality Monitoring process**

The PHC program will utilise a Data Safety and Monitoring Board to monitor the difference between groups and will be able to cease the study if it is deemed appropriate. The DSMB will also review both and adverse events Serious Adverse events. The DSMB will develop a charter upon formation and determine appropriate statistical measures to inform decision making.

Please refer to the Adverse Events and Quality Management Plan document and the quality monitoring excel spreadsheet in the appendices for more detail

### **Governance**

The Barwon Health Personalised Health Care (BH Personalised Health Care) service pilot will sit in the directorate of Community Health and Rehabilitation Services (CH&RS). Along with the other programs in this directorate, it aims to support people in the community, transitioning back to the community and avoiding hospitalisation wherever safe and possible. Governance for clinical care, safety, quality and performance reporting is the accountability of CH&RS Executive team and Executive Director.

This pilot will be operated in conjunction and close partnership with the Medical Services directorate, with medical input, oversight of patient care and treatment coming from specialist consultants within Respiratory Medicine and Endocrinology.

### **Evaluation and Monitoring**

Barwon Health and its associated partners have been approved to evaluate the program by the Department of Health through this research methodology.

### **Data Sources/Collection**

Data will be collected from hospital data systems, medical records of participating patients and survey / questionnaires/hospital admission data and interview. Data will be stored in password protected files on Barwon Health Computers. Any paper based patient data will be stored in locked cupboards / drawers for a period of seven years. At the conclusion of this period all paper based records will be destroyed.

### **Data Security and Storage**

Clinical Data for the intervention group will be stored in the purchased software system and backed up on a Barwon Health Server. The clinical data will be transferred into the clients Digital Medical Record into a separately labelled section titled "BH Personalised Health Care". This will enable clinical staff treating the client in other parts of the organisation to be able to see the client's data and results as required. A flag indicating the client is enrolled in this pilot will be placed in the alert section of the Digital Medical Record.

The senior staff of the Emergency Department will be provided with education of the pilot and the information technology system. The senior staff (NUM and ANUM's) will be able to access the

Personalised Health Care system; this will ensure immediate access to daily clinical data if and as required via the BH Information Technology system.

It should be noted that this pilot program provides support and monitoring to clients over and above the current support structures that are available in the community for a client with chronic disease therefore the risk to any clients care when on the program is minimal.

**Informed Consent**

Participants who agree to participate in the trial will be asked to sign a consent form. Only participants who sign the consent form will be able to participate. Participants can leave the trial at any point. (Please see appendix B for consent form).

The PICF will be entered into the patients DMR.

**Confidentiality and Privacy**

For intervention group members confidentiality of all patient data will be maintained in accordance with normal hospital procedures. For additional data regarding health literacy and hospital utilization for both control and intervention groups the data will be stores in password protected files.

All staff working with the data will have signed Barwon Health’s Client Data Confidentiality agreement . Data Linkage will be completed by Barwon Health’s “Health information Services - business analysis manager.

All interview and survey data collected will be de-identified and use pseudonyms chosen by the participant. A code sheet linking the participant’s pseudonym and their real identity will be stored away from the data on a secure password protected server.

Surveys will be sent to the patients address with marked Patients age in years, gender and HEIQ initial results noted in a code box for office use. No other identifying information will be collected on the survey. As such, the surveys will be non-identified.

All data will be stored on a secure password protected hard drive with the researchers being the only ones with access. The drive will be stored within the Barwon Health computer system. All hard copy notes will be kept in a locked cupboard in a locked room when not in use. All data will be destroyed seven years following the last publication of the project.

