#### **Qualitative and interview Recruitment**

A convenience sample of participants in the intervention group will be recruited. Potential participants will be sent an invitation (Appendix D), via the post, to fill in the survey and/or participate in an interview with the researcher and assistant. A consent form (Appendix D) for participating in the interview is attached to the letter, while return of the completed survey will be

taken as consent to participate in the survey.

Follow up with the intervention participants will be made ten working days after the letter has been sent to determine if they are interested in participating.

**Note:** Nurses employed to work on the program will enrol and consent the patients. Nurses will be provided with training regarding informed consent from Assoc [name]. Consultant physicians will not be identifying, consenting or enrolling participants onto the study and hence any relationship of dependency issues would be mitigated.

**Participant recruitment:** (please see Appendix A for flow chart)

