Data Collection Method for the post intervention evaluation will consist of a survey (Appendix G) made available for all study intervention participants. All patients will be mailed an invitation (Appendix F) to participate in the post intervention evaluation. Participants, regardless of their status within the program, eg. Completed, currently still receiving the intervention, or completed and still receiving the intervention will be offered the opportunity to respond about their experience by survey, the surveys will be returned to the Personalised Health Care mail box.

An invitation will also be extended to study intervention participants to participate in an interview. Invitations for this component of the evaluation will continue until n=12. The study population is seen as homogeneous in their experience. All are living with chronic conditions and all have received the same service intervention over the previous 12 months. It is expected that interviews with approximately 12 participants will produce saturation in response themes and provide evidence enough to produce the required result. Participants regardless of their status within the program, eg. Completed, currently still receiving the intervention, or completed and still receiving the intervention will be offered the opportunity to participate until n=12.

The interview will be conducted using the interview schedule (Appendix H). All interviews will be pre-booked with the patient and an assistant. The assistant will be a staff member from the Personalised Health Care team. The researcher will introduce themselves to the interviewee and will be present in the room to take field notes during the interview. The interview scheduled questions will be asked by the assistant. All interviews will be digitally recorded for verbatim transcription post the interview. Patients will be offered the option of having the interview undertaken using the facility of video conferencing that has been employed by the program or by arranging a time for the assistant and researcher to visit their home or other agreed meeting place.

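### The experience survey is described both as coded with an identity key and as non-identified, while its markings would let most forms be matched to one patient and it is returned to the service being evaluated

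*Protocol*

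**What the plan says.** Two adjacent paragraphs of the Protocol, Confidentiality and Privacy, describe the survey data.

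- The first states: "All interview and survey data collected will be de-identified and use pseudonyms chosen by the participant". It adds that the code sheet linking each participant's "pseudonym and their real identity will be stored away from the data on a secure password protected server".
- The second states: "Surveys will be sent to the patients address with marked Patients age in years, gender and HEIQ initial results noted in a code box". It continues "No other identifying information will be collected on the survey" and concludes "As such, the surveys will be non-identified".

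The Protocol, Staffing and Reporting, says that the survey is "made available for all study intervention participants", whether they have completed the program or are still receiving it, and that "the surveys will be returned to the Personalised Health Care mail box". The sample size section caps the intervention group at 200. The list of baseline measures includes the Health Education Impact Questionnaire (HEIQ) for both the diabetes and the COPD cohorts.

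**The concern.** Data held under a pseudonym with a key to real identity are coded and can be re-identified. Data described as non-identified should not be traceable to a person. One survey cannot be both. The second description is also doubtful in itself, because exact age, gender and a personal baseline questionnaire result make a fine-grained combination in a group of at most 200, and the study holds the same items by name.

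The return route adds to this. Patient experience is a listed evaluation criterion in the synopsis. The forms go to the mail box of the service whose performance they describe, and some respondents still depend on that service. A patient who sees personal details in a code box on a form going back to the care team has some reason to answer kindly. The protocol recognises dependency elsewhere: under Qualitative and interview Recruitment it keeps consultant physicians out of identifying, consenting and enrolling for this reason. It describes no similar safeguard for the survey returns.

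**Working it through.** The protocol gives no figure on this point, so there is none to reproduce. The check has a textual part and an illustrative calculation.

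**Textual comparison**

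| Question | First paragraph | Second paragraph |
|---|---|---|
| What labels the form? | A pseudonym chosen by the participant | Age in years, gender, initial HEIQ results; nothing else identifying |
| Is there a key to identity? | Yes, a code sheet stored apart | None mentioned |
| Resulting status | Coded, re-identifiable | Non-identified |

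The pseudonym route also lacks a described step for the survey. Forms are posted out and their return counts as consent, so it is not stated when someone who answers only the survey would choose a pseudonym. The code box is specific to the person, so whoever prepares the mailing must match it to a named addressee.

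**How far the markings identify a person**

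From the protocol: at most N = 200 clients surveyed; markings are age in years, gender and HEIQ results; HEIQ is held by patient at baseline.

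Assumed, because the protocol does not give them: ages roughly normal, mean 67, SD 10 to 15; a 55/45 gender split; K equally likely HEIQ levels. How the results are noted (bands, subscales or totals) is not stated, so K is varied.

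If a cell (one age, one gender, one HEIQ level) has probability p, a client in it is alone with probability (1 − p)^199. The expected share of clients who are unique is the sum over cells of p × (1 − p)^199.

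One cell as an example, at SD 10: the probability of age 67 is about 0.040.

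- Age and gender only, for the 55% gender: p = 0.040 × 0.55 = 0.022, and (1 − 0.022)^199 ≈ 0.012. Such a client is almost never unique.
- With 10 HEIQ levels: p = 0.0022, and (1 − 0.0022)^199 ≈ 0.645. Even at the commonest age, such a client is unique about two times in three.

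Summed over all cells:

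| HEIQ levels K | Unique, age SD 10 | Unique, age SD 15 |
|---|---|---|
| 1 (age and gender only) | 12% | 18% |
| 10 | 76% | 82% |
| 50 | 95% | 96% |
| 100 | 97% | 98% |

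Equally likely levels favour uniqueness. With a bell-shaped 10-level score (SD 1.5 to 2 levels) and ages of mean 68, SD 11, the share is 64 to 70%. For a 10-level score the range is therefore about 64 to 82%. Pairing age SD 10 (mean 67) with the narrower score (SD 1.5) brings it to about 61%, which does not change the conclusion. The denominator is all clients surveyed, not only those who reply, because a form is matched against the whole group.

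**The case against.** Several stronger readings are tempting but lack support.

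- **No study code, so links to diagnosis or program status are lost.** The protocol does provide a pseudonym key covering survey data. If it applies, the links are kept. If it does not, the traceability shown above would recover most of them, though only by breaking the non-identified description.
- **Diagnosis and status are missing from the form.** The survey itself (Appendix G) is not shown and may ask for them.
- **Repeat returns cannot be recognised.** The follow-up rule says "Follow up with the intervention participants will be made ten working days after the letter has been sent", to ask about interest. No second mailing of the survey is stated.
- **The response rate is unavailable.** The survey goes to all intervention participants, so the number mailed is known and returns can be counted.
- **Patients are told something untrue.** The letter and consent for the survey (Appendix F) are not shown. Only the protocol's own description can be faulted.

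It is also fair to say that matching needs access to individual baseline data. The protocol limits access to the stored data to the researchers, requires a staff confidentiality agreement and locks away hard copy. It does not say who opens the mail box, and favourable answering is inferred, not shown. These safeguards lower the chance of misuse but do not make the forms non-identified. Separation between service and study is also limited: under Staffing and Reporting, the program Manager oversees research processes and data collection.

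**Conclusion.** The point holds. The protocol describes the survey in two ways that cannot both be true, and the non-identified label is wrong for a form carrying exact age, gender and individual HEIQ results. For anyone holding the baseline data, most forms would point to one person once even a coarse HEIQ score is added. The percentages are illustrations that rest on assumed ages, gender split and score distribution. That most forms would be matchable holds across the ranges tried for a score of 10 or more levels.

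Returning the forms to the service under evaluation gives a plausible route to favourable answers, of unknown size. The consequence is confined to the post-intervention experience survey. Randomisation, the hospital utilisation outcomes, and the quality-of-life and self-management measures are untouched. It merits correction because the remedy is cheap and patient experience is a stated evaluation criterion.

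**What to change.** Rewrite the two paragraphs under Confidentiality and Privacy so that one description applies.

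- **Coded option.** Replace the age, gender and HEIQ markings with a random study code. Have the key held outside the program team, for example by the data-linkage role already named in that section. Merge the baseline variables from the database, and describe the surveys as coded and re-identifiable.
- **Anonymous option.** Remove exact age and individual HEIQ results. The non-identified description can then stand, but individual answers can no longer be linked to baseline data.

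Under either option, send returns to someone outside the care team and amend Staffing and Reporting to match.

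The cost is a change to the form, the return address and the wording, with notification to the ethics committee. Under the coded option the protocol must also acknowledge that the key holder can re-identify respondents.
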